APPENDIX 1. SUMMARY OF INVESTIGATIONS, TREATMENT AND ASSESSMENTS		
	24	

GLOSSARY OF ABBREVIATIONS

KEYWORDS

Electronic monitoring device (EMD)
Novel electronic monitoring device (NEMD)
Compliance
Adherence
Children
Asthma

STUDY SUMMARY

TITLE	A feasibility study to assess novel electronic monitoring devices for monitoring adherence in children with asthma
DESIGN	A mixed method (quantitative and qualitative) open label, block randomised feasibility study
AIMS	
 1. To assess the feasibility of 4 novel electronic monitoring devices in children aged 6-16 years with asthma, in terms of usability and acceptability by patients/ guardians and healthcare professionals (qualitative study) 2. To evaluate the accuracy of these devices and assess whether they impact on asthma control (quantitative study)
OUTCOME MEASURES	
Primary outcome: Acceptability and usability of devices to participants and healthcare professional at Royal Brompton and Harefield NHS foundation Trust (RBHT)
 
Secondary outcomes:
 
 1. Accuracy of the adherence data collected from the devices. 2. Effect on asthma control as measured by asthma control test (ACT) or childhood asthma control test (cACT) score; exhaled nitric oxide (FENO), spirometry (FEV1) and bronchodilator reversibility (BDR).
POPULATION	Children aged 6-16 years with asthma on inhaled corticosteroid therapy.
ELIGIBILITY	Children aged 6-16 years with a diagnosis of asthma on inhaled corticosteroids who are being treated or followed up by the paediatric respiratory difficult asthma clinic at Royal Brompton hospital.
DURATION	Up to 16 weeks

1. INTRODUCTION

1.1 BACKGROUND

Asthma affects 1.1 million children in the UK and is a significant economic burden to the NHS (NHS information centre). Despite advances in care, acute asthma attacks are one of the most common presentations to the Emergency Department. Persistent symptoms and frequent exacerbations can impact negatively on quality of life and sadly children still die from asthma. The National Review of Asthma Deaths (NRAD) included 28 deaths in young people under the age of 20 years. The report highlighted that poor adherence to medical treatment, especially in children is one of the most important reasons for apparent treatment failure and recommends that adherence should be continually monitored.

Suboptimal adherence has been linked to risk of exacerbations, hospital admissions, reduced quality of life and asthma related deaths (1)(2)(3). Once poor adherence has been identified, there is little evidence of benefit of adherence interventions(4).

Adherence to inhaled corticosteroids (ICS) in asthma ranges from 30-70% (5). Patient or parent report is inaccurate, over-estimating the treatment taken. and physician assessment little better than chance (2) (6).Objective measures of medication use, such as prescription refill rate are a little more accurate; however even if inhalers are picked up they are not necessarily taken.

Recently, there has been an increase in the use of electronic monitoring devices (EMD) which can be used to monitor adherence to inhaled treatments. The EMD's are available with or without reminders and provide important data on activation, timing of the activation and the number of doses activated. They have the potential to transform care for people with asthma (7) (8). EMDs have two key roles to play; enabling healthcare professionals to interpret control in the context of know adherence and inform decision making and as a tool for the patient to aid self-management and improve adherence. We have demonstrated the role of currently available EMDs in supporting the decision making process and identifying children with severe asthma (9).

The improvements across the range of asthma control measures suggested that adherence improved because the participants were aware they were being monitored. This supports the second role of EMDs as an intervention for adherence.

Studies which have compared EMDs with standard care have demonstrated significant improvements in adherence in the EMD arm (30% versus 85% and 49% versus 70%), however, they have shown only modest improvements in asthma control (8) (10). This may in

part be due to the limitations of current EMDs. Although they measure activation they give no information on whether the inhaler was used correctly, or even if inhaled at all. This would provide plausible explanation for limited clinical benefit despite large differences in adherence. Furthermore, in these studies adherence remained suboptimal (<80%) in the majority despite monitoring. This is unsurprising as EMDs only address some of the reasons for poor adherence.

Determinants of poor adherence

The practicalities and perceptions (PAPA) model (5) divides the numerous reasons for poor adherence into two broad themes. Practical barriers include poor technique and forgetfulness. This leads to unintentional non adherence: the patient wants to take the treatment but is limited by their capabilities. Perceptual barriers lead to intentional non adherence: the patient is not motivated to take medication because of their concerns. Thus, ongoing poor control despite documented good adherence (with current EMDs) may be a result poor technique (practical barrier) or deliberate manipulation because of concerns about treatment efficacy or side effects (perceptual barrier).

1.2 RATIONALE FOR CURRENT STUDY

A number of platforms are currently in development which will enable the clinician to monitor both activation and inhalation, thus ensuring more accurate estimates of adherence and better addressing practical barriers to adherence. Currently the utility and feasibility of these platforms and acceptability to children, their families and healthcare professionals is not known.

Often devices are formulated for adults then extrapolated to children (11),(12) , highlighted the need and benefits of user involvement in the design of EMDs in children, particularly adolescents with asthma and the need to consider all aspects of medical design including data, usability and aesthetics in future studies to maximise the chance of success.

The benefits of using user feedback in adherence monitoring have been highlighted in many studies some using focus groups other using one to one interviews(11), (13),(14). Other studies have recommended that robust technology support to troubleshoot technological issues arising during the intervention should also be taken into consideration into the feasibility of using EMD's for monitoring adherence (14).

We propose to conduct an open label, block randomised, mixed methods, feasibility study to assess the accuracy, usability and acceptance of four novel electronic monitoring devices

(NEMD) that monitor both activation and inhalation thereby providing information on dose taken and technique.

We will conduct face to face focus group or one to one interviews using semi-structured questions to evaluate user feedback and assess the accuracy of the NEMD's used. Additionally, asthma control will be assessed as part of routine clinical care using our difficult asthma protocol.

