2. STUDY OBJECTIVES

Research question: Which novel electronic monitoring device (NEMD) (measuring both inhalation & activation) is the most feasible to use as a tool for monitoring adherence in children aged 6-16 years with asthma in terms of accuracy, usability and acceptability?

Aim: To conduct a feasibility study looking at four new electronic monitoring devices to monitor adherence in children with asthma aged 6-16 years prescribed inhaled corticosteroids.

Our primary objective is to assess which novel electronic monitoring device is the most feasible to use as a tool for monitoring adherence in children with asthma, in terms of its perceived accuracy, usability and acceptability by patients/guardians and healthcare professionals by using a face to face focus group discussion meeting or one to one interviews.

For the purposes of this study feasibility is the overarching term used to assess if the devices are capable of being used in clinical practice to monitor adherence.

Accuracy of the device will be assessed by capturing usable data from the devices. Usability of the device will be assessed from the focus group or one to one interviews encompassing ease of use, time taken, problems encountered, easy to learn to use the device.

Acceptability will also be assessed from the focus group discussions or one to one interviews in terms of aesthetically pleasing, liked the device, fits in with day to day living.

Our secondary objective is to evaluate the effect on asthma control as measured by asthma control test (ACT) or childhood asthma control test (CACT) score; exhaled nitric oxide (FENO), spirometry (FEV1) and bronchodilator reversibility (BDR)

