Where possible a second researcher from University College London (UCL), [name] will sit in the focus groups discussion and interviews to ensure there is no bias.

The conversations from the focus group and one to one interviews will be transcribed and coded into themes. We will utilise an external company for transcribing the conversations called 1st Class. <https://www.1stclass.uk.com/>

Analysis

Qualitative:

The focus group and one to one interviews will be audio recorded, transcribed and put into themes to conduct an inductive thematic analysis. 25% of the transcripts (8) will be double coded by an independent researcher from UCL, [name], experienced in qualitative research to ensure that the correct themes have been used and to ensure that there is no bias.

The focus group and one to one interviews will be used to assess the usability and acceptability of the devices

Quantitative:

[figure not shown]
The amount of usable data from each device will be quantified and compared.

This will provide data on the perceived accuracy of the device.

The quantitative and qualitative results will be amalgamated and an evidence report prepared to assess the feasibility of each device.

An expert panel will be convened to select the most appropriate device to take forward to a larger randomised controlled trial to assess the impact of the device on adherence in children with asthma.

REFERENCE DIAGRAM

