The focus group interviews will be used to assess the usability and acceptability of the devices

➤ Quantitative data

The amount of usable data from each device will be quantified and compared.

This will provide data on the perceived accuracy of the device.

Additionally, data on asthma control and quality of life will be assessed.

These will be analysed quantitatively statically using the Statistical Package for the Social Services (SPSS). Data will be tested for normality using visual inspection, histograms and Kolmogorov-Smirnov testing. Parametric tests will be used if the data is normally distributed. If the data is not normally distributed or there are only small numbers non parametric tests will be used or the data will be logarithmically transformed. The significance levels for all tests will be set at <0.5.

Comparative analysis of variance between 2 groups for continuous data will be performed using the student's t test for normally distributed data and the Mann Whitney U tests for non normally distributed data and for more than 2 groups the ANOVA or Kruskal Wallis respectively. A comparison of the proportions between groups will be performed using the Pearson Chi 2 tests.

The quantitative and qualitative results will be amalgamated and an evidence report prepared to assess the feasibility of each device.

An expert panel will be convened to select the most appropriate device to take forward to a larger randomised controlled trial to assess the impact of the device on adherence in children with asthma.

Data and all appropriate documentation will be stored for a minimum of 10 years after the completion of the study, including the follow-up period.

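### The only analysis specified for the device data is an undefined amount of usable data; no adherence or correct-inhalation percentage is pre-specified, although recording inhalation is the reason for testing these devices

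*Combined protocol and SAP*

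**What the plan says.** Section 1.1 says of the monitors now in use: "Although they measure activation they give no information on whether the inhaler was used correctly, or even if inhaled at all". It offers this as a possible reason why large gains in adherence brought only modest gains in control. Section 1.2 then proposes four devices "that monitor both activation and inhalation thereby providing information on dose taken and technique". The research question in section 2 asks which device "measuring both inhalation & activation) is the most feasible to use as a tool for monitoring adherence".

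The Study Summary gives the first secondary outcome as "Accuracy of the adherence data collected from the devices". Section 2 makes this operational: "Accuracy of the device will be assessed by capturing usable data from the devices". The analysis text in section 3, repeated in section 7, is one sentence: "The amount of usable data from each device will be quantified and compared". Both sections then interpret the result: "This will provide data on the perceived accuracy of the device". The other quantitative endpoints are asthma control and quality of life.

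Under section 3, adherence data are downloaded in week 1 for the video arm, in week 4 for all devices as a check on function, and at study end. Appendix 1 marks downloads at 7 days, 4 weeks and up to 16 weeks. The interview and quantitative results are merged into a report, from which an expert panel chooses a device for a "larger randomised controlled trial to assess the impact of the device on adherence in children with asthma".

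**The concern.** The new feature of these devices is that they detect inhalation as well as activation. The specified analysis does not ask whether that feature delivered anything. An amount of data is a volume. Without a definition of *usable* it may or may not require an inhalation, and without a denominator it is not adherence. The panel is choosing a tool for a trial whose subject is adherence, yet its report need contain no adherence percentage and no statement of how often each device captured an inhalation. The data that would answer both questions are already being downloaded.

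**Working it through.** **1. A plan figure to reproduce.** There is none for adherence or inhalation. The only sample-size figure, 29 participants in section 7, concerns interview themes. It reproduces: the chance of seeing a theme of 10% prevalence at least twice is 0.785 with 28 participants and 0.801 with 29. It has no bearing on the device data.

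**2. Tracing inhalation and adherence through the plan.**
- Rationale (1.1, 1.2) and research question (2): both activation and inhalation are named.
- Outcomes (Study Summary): accuracy of adherence data, with no unit, measure or reference.
- Definition (2): accuracy becomes capture of usable data. Inhalation is no longer mentioned.
- Conduct (3): technique is reviewed on video clips, with a documented nurse call if it is wrong; the INCA audio is described as allowing technique to be assessed. Neither is turned into a rate.
- Analysis (3, 7): amount of usable data only.
- Schedule (5, Appendix 1): adherence monitoring and downloads, with no summary measure.

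The link from rationale to analysis breaks at the definition of accuracy.

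**3. Effect of having no denominator.** Section 3 allots 10 children to Smartinhaler Plus, 5 to Flo-Tone/Rafi-tone, 5 to INCA and 10 to video. Assume 2 prescribed doses a day, which the documents do not state. Sixteen weeks is then 16 × 7 × 2 = 224 doses per child. With every dose recorded, a group of 10 yields 10 × 224 = 2,240 records and a group of 5 yields 5 × 224 = 1,120. Adherence is the same and the total differs twofold. Per child the same problem arises from follow-up time: monitoring lasts up to 16 weeks, and section 4.4 allows use of data from a withdrawn child with more than 8 weeks. Eight weeks is 8 × 7 × 2 = 112 doses, half of 224. Both ratios hold for any dose frequency common to the children compared.

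**4. Effect of having no inhalation requirement.** This is an illustration on assumed values only, with 224 prescribed doses.
- Device A logs 95%: 0.95 × 224 = 213 records. If 0% to 50% of them carry an inhalation signal, 0 to 106 doses are confirmed (0% to 47.5% of prescribed).
- Device B logs 85%: 0.85 × 224 = 190 records. If 95% carry a signal, 181 doses are confirmed (80.8%).

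If any logged record is usable, A has more data. If a usable record must contain an inhalation, B has more. The text does not say which reading applies.

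**5. Precision of the proposed figures.** The half-width of a 95% CI for a mean per-child percentage is t(0.975, n−1) × SD / √n. Assume a between-child SD of 15 to 30 percentage points.
- n = 10, t = 2.262: 11 to 21 points.
- n = 5, t = 2.776: 19 to 37 points.

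The figures can describe each device. They will not separate devices unless the differences are large.

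**The case against.** The study calls itself largely qualitative and its primary outcome is acceptability and usability. The panel weighs interviews and asthma control too, and the research question names inhalation, so *usable* may well be meant to include it. All of that stands, and it limits the consequence. It does not fill the gap, because accuracy is in the research question and is a listed outcome, and nothing obliges the report to show inhalation capture.

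Four stronger readings are tempting and should not be drawn.
- *A device that misses inhalations could come first.* There is no ranking rule, and the counts in step 4 are assumed. The scenario also does not fit every device: as described in section 3, Flo-Tone sounds on correct use and the video films the dose, so neither is an activation counter.
- *Adherence will never be computed.* The data are downloaded and checked, and a figure under the quantitative heading in section 3 could not be read. Section 7 repeats the analysis in full text and adds no adherence measure. The documents support *not specified for analysis* and no more.
- *Activation minus inhalation would show whether the device works.* It would not. The difference mixes missed detection with a child's truly poor technique, and the plan has no reference standard.
- *The study fails because it gives no SD for planning the next trial.* No stated aim is to supply one.

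**Conclusion.** The concern holds as a gap in pre-specification that affects what the study can answer. As written, the device data can meet the analysis plan without showing whether any device captures inhalation or what adherence it records, so secondary outcome 1 and the accuracy part of the research question are not addressed. The size of any resulting error cannot be derived, because the documents give no capture or adherence rates. The twofold differences in raw amount follow from group size if records are totalled by device, or from follow-up time if they are counted per child; the plan does not say which. The gap should be closed before the data are analysed, but it does not undermine the qualitative primary outcome.

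**What to change.** In the analysis text of sections 3 and 7, replace the raw amount with three per-child figures, summarised descriptively by device with 95% CIs and with the child, not the dose, as the unit:

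1. recorded doses / prescribed doses;
2. the share of recorded doses with an interpretable inhalation signal (for video, inhalation visible on the clip), as the data-capture measure;
3. doses with a correct inhalation / prescribed doses, as the adherence measure.

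List (2) and (3) under secondary outcome 1 in the Study Summary. State in advance what counts as a correct inhalation for each device, since flow, sound, audio and video do not apply one common criterion.

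Report activation and inhalation separately. Where a device does not record a component, mark it as not measured and keep its other records. This matters for Flo-Tone/Rafi-tone, for which section 3 describes no separate activation record; a rule requiring a time-stamped activation could score it zero by definition. Give the activation-minus-inhalation difference only where both are recorded, as a description of how the adherence estimate changes and not as a test of accuracy.

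**Cost.** The device data are already downloaded, so the main work is wording and scoring. On the 224-dose assumption the video arm could hold up to 10 × 224 = 2,240 clips; section 3 already provides for nurse review of clips, so part of the extra work is recording the result. The INCA audio needs analysis. Section 5 takes drug history at Visit 1 only, so changes in prescribed doses must be noted to keep the denominator right. The estimates will be imprecise, and a device that records only one component will look less favourable.

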2. STUDY OBJECTIVES

Research question: Which novel electronic monitoring device (NEMD) (measuring both inhalation & activation) is the most feasible to use as a tool for monitoring adherence in children aged 6-16 years with asthma in terms of accuracy, usability and acceptability?

Aim: To conduct a feasibility study looking at four new electronic monitoring devices to monitor adherence in children with asthma aged 6-16 years prescribed inhaled corticosteroids.

Our primary objective is to assess which novel electronic monitoring device is the most feasible to use as a tool for monitoring adherence in children with asthma, in terms of its perceived accuracy, usability and acceptability by patients/guardians and healthcare professionals by using a face to face focus group discussion meeting or one to one interviews.

For the purposes of this study feasibility is the overarching term used to assess if the devices are capable of being used in clinical practice to monitor adherence.

Accuracy of the device will be assessed by capturing usable data from the devices. Usability of the device will be assessed from the focus group or one to one interviews encompassing ease of use, time taken, problems encountered, easy to learn to use the device.

Acceptability will also be assessed from the focus group discussions or one to one interviews in terms of aesthetically pleasing, liked the device, fits in with day to day living.

Our secondary objective is to evaluate the effect on asthma control as measured by asthma control test (ACT) or childhood asthma control test (CACT) score; exhaled nitric oxide (FENO), spirometry (FEV1) and bronchodilator reversibility (BDR)

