All children will be issued with a novel electronic monitoring device which will be attached to the child's usual inhaler or require an app on their mobile phone as described above. Parents and children will be provided information and advice on the use of the novel electronic monitoring device and asked to conduct up to 16 weeks of home monitoring using their allocated NEMD on their first visit.

Information on how to contact the team in case of any problems will be related to the participant in both oral and written form.

The data will be stored electronically and downloaded at the next clinic visit.

Contact by telephone will be made at day 7-14 to ensure that the device is working and to answer any other queries then at week 6-7 to determine if the device is being used appropriately and to answer any related questions.

Week 1 - for the rDOT arm, adherence data will be downloaded to check for consistencies in inhaler technique. If inhaler technique is inaccurate, the participants will be called by the respiratory nurse specialists to advise on correct technique. This will be documented as part of the data collection.

Week 4 – All devices, adherence data will be downloaded and checked to ensure that the devices are working correctly.

Visit 2: up to 16 weeks of adherence data collection

Routine clinical care assessments will be carried out at the end of the study period as below, including asthma control test (ACT) or the childhood asthma control test (cACT), exhaled nitric oxide and spirometry (FEV1 and BDR) .

Adherence data will be downloaded at the end of the study period and stored electronically.

Visit 3: Focus group or one to one interviews

The participants and their carers will be invited to a face to face focus group interview, or a one to one interview, depending on their availability at the end of the study period. The focus group and one to one interviews will utilise a semi structured questionnaire, to provide qualitative feedback on the acceptability and usability of the devices.

A separate focus group meeting will also be conducted with the paediatric respiratory nurses who are part of the MDT to assess their views on the devices used as they routinely provided all asthma devices and are also involved in downloading data from other devices that we would use as part of routine care (smart-inhaler). They will also be consented to take part in the study

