5. ASSESSMENT AND FOLLOW-UP

No study assessments will take place until written informed consent and age appropriate assent is obtained.

Routine clinical care data will be collected at the baseline visit and at the end of the study as follows:

Routine clinical care monitoring tests

Routine clinical care test to assess	Test	Visit 1: Study entry	Visit 2: completion of study
Asthma control	ACT/cACT	√	√
Spirometry	FEV ₁ /FVC/BDR	√	√
Inflammation	FeNO	√	√
Asthma related quality of life questionnaire	PAQLQ/PACQLQ	√	√
Prescription uptake		√	√
Drug history		√	
Data downloaded from device: Routine clinical care would be to download from smartinhaler	Data downloaded from new device		√

The main difference between data collection in this study and routine clinical care monitoring is that data will be downloaded from the new devices (NEMD) in comparison to the current smartinhaler device

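### Device accuracy is measured only by the amount of usable data, which shows data capture and cannot support a conclusion on accuracy

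*Combined protocol and SAP*

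**What the plan says.** Accuracy appears in the protocol in several forms.

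- **Study Summary, secondary outcome 1:** "Accuracy of the adherence data collected from the devices".
- **Section 2, research question:** which device is the most feasible, judged on accuracy, usability and acceptability.
- **Section 2, primary objective:** feasibility judged "in terms of its perceived accuracy, usability and acceptability by patients/guardians and healthcare professionals", by focus group or one-to-one interview.
- **Section 2, definition:** "Accuracy of the device will be assessed by capturing usable data from the devices".
- **Section 7, Quantitative data (also section 3, Analysis):** "The amount of usable data from each device will be quantified and compared", followed by "This will provide data on the perceived accuracy of the device".
- **Section 1.2:** the focus groups or interviews are to gather user feedback and also to assess device accuracy.
- **Section 3, Visit 3:** the same interviews are "to provide qualitative feedback on the acceptability and usability of the devices"; accuracy is not mentioned.

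The quantitative and qualitative results are then combined in an evidence report, and an expert panel selects one device for a larger randomised trial (sections 3 and 7). Neither 'usable' nor a denominator is defined.

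**The concern.** Accuracy is agreement between what a device records and what happened. An amount of downloaded data makes no such comparison. A device can deliver complete files that misstate the doses, or correct records with gaps.

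This matters for this study in particular. Section 1.1 faults current devices because they do not show whether the inhaler was used properly or inhaled from at all, and section 1.2 justifies the new devices by more accurate estimates of adherence. The plan as written does not test that property, yet it would report a result under the name of accuracy. The panel that selects the device would read that result. Two different quantities, one downloaded and one elicited in interviews, also share the name perceived accuracy.

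**Working it through.** **1. Is there a planned figure to reproduce?** Not for accuracy: no effect size, margin, SD or power is given. The only sample-size figure is 29 participants, to see a theme of 10% prevalence at least twice with 80% probability. It reproduces: 1 − 0.9^29 − 29 × 0.1 × 0.9^28 = 0.801, against 0.785 for 28 participants. It concerns interview themes and has no bearing on accuracy.

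**2. What the download amount contains.** For one child, let T be doses actually taken, s the share of them recorded correctly, F the number of wrong records (false or misread), and c the share of records that reach the database in usable form. Then

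U = c × (s × T + F).

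The plan observes U. Accuracy lies in s and F, and neither can be recovered from U while T is unknown.

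An illustration with assumed values, reading 'usable' as 'uploaded':

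- Device X: s = 1, F = 0, c = 0.80. U = 0.80T, and correct records = 0.80T.
- Device Y: s = 0.70, F = 0.30T, c = 1. U = 1.00T, and correct records = 0.70T.

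The order on U is the reverse of the order on correct records. This shows that the two quantities can separate. It does not say how often they would.

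**3. Does the plan hold a measure of T elsewhere?**

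- Nurse review of video (section 3) checks technique, in the rDOT arm only.
- The week-4 download (section 3) checks that devices are working.
- The telephone calls at day 7–14 and week 6–7 ask whether the device works and is used appropriately.
- "Prescription uptake" is collected at both visits (section 5) but is not linked to accuracy, and it is not a count of doses taken.

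None gives doses taken for comparison with the record across the four devices.

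**4. Does the measure also carry adherence and follow-up time?** That depends on the undefined terms.

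| Reading of the amount of usable data | Reflects adherence? | Reflects length of monitoring? | Measures accuracy? |
|---|---|---|---|
| Count of usable records | Yes | Yes (monitoring lasts up to 16 weeks) | No |
| Records as a share of prescribed doses | Yes | Largely removed | No |
| Days with a record as a share of days monitored | Only if a no-dose day counts as missing | Largely removed | No |
| Readable files as a share of all files | Little | Little | No |

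The last column is the same in every row. The adherence component is therefore conditional, while the absence of an accuracy measure is not.

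**5. Perceived accuracy.** Section 2 obtains it by interview; sections 3 and 7 obtain it from the download amount. Section 1.2 has the interviews assess accuracy; section 3 (Visit 3) limits them to acceptability and usability. A quantity of data is not a perception, and these statements cannot all stand.

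**6. Early failures.** Under section 4.4, a withdrawn child's data are not used unless more than 8 weeks were collected. With 10 children per block, and 5 on each of the two half-block devices, a few exclusions after device failure could raise a device's apparent capture without leaving a trace.

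**The case against.** The strongest defence is that this is a feasibility study. Its primary outcome is acceptability and usability, accuracy is secondary, and data capture is a proper thing for such a study to measure. The panel also sees the qualitative results. All of that stands, but it defends the measurement and not its name. A second defence is that a misread record might be judged unusable. That would need a rule and some independent knowledge of the dose; the plan gives no rule, and outside the video arm it describes no such knowledge.

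A reader might infer more than the documents support:

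- *That the trial asks which device is most accurate.* It asks which is most feasible, with accuracy one of three components.
- *That the plan would rank a high-yield, inaccurate device first.* There is no ranking rule; results are combined and a panel decides. The example under working rests on assumed rates.
- *That adherence alone makes data amounts differ 2.3-fold (70/30).* The 30–70% in section 1.1 is a general range for inhaled corticosteroids, whereas every child here is monitored. The monitored arms cited in section 1.1 had 85% and 70%, a ratio of 1.2. Either ratio matters only under some readings of 'usable'.
- *That prescription uptake could serve as the accuracy check.* Inhalers already held at Visit 1 mean that supply collected between visits is not an upper bound on doses. Section 5 names no dose counts or collection dates. The check would also miss most over-recording: if supply equals prescribed doses, 70% adherence with 30% over-recording gives 0.70 × 1.3 = 91% of supply, which raises no flag. It cannot detect missed records or misjudged inhalation.

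**Conclusion.** The point holds: carried out as written, the plan yields a result on data capture under the label of accuracy, and no conclusion on the accuracy of any device follows from it. This rests on the text alone and is true under every reading of 'usable'. That the measure also reflects adherence and monitoring time is possible but depends on definitions the plan does not give.

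The effect on device selection cannot be sized from the documents. A probability of choosing differently would need capture rates, the spread of adherence between children and a decision rule, none of which is stated. What can be said is that the panel could treat data capture as accuracy, and that the sections on perceived accuracy contradict each other and must be reconciled.

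**What to change.** 1. **Rename and define.** In the Study Summary, section 2, section 3 (Analysis) and section 7, call the download outcome 'data capture': days with a readable device record divided by days the device was issued. Count a day with no dose on a working device as captured, so that adherence does not re-enter. Where a device records only when used, as with video clips, report days without a record separately as 'no dose or no capture, cannot be distinguished'.
2. **Account for everyone.** Show all randomised children by device, and state how many are left out under the 8-week rule in section 4.4. This needs counts of children and not their withheld data, and it keeps early device failures visible.
3. **Separate perceived accuracy.** Report it from the focus groups and interviews only. Reconcile sections 1.2, 2, 3 and 7 accordingly, and make sure the interview guide covers it.
4. **Limit the claim.** State in the evidence report that the study does not estimate the true accuracy of any device.

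The cost is protocol wording, an addition to the interview guide and a descriptive table by device; no new study procedure is needed. The downside is a weaker claim about accuracy.
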